3.3.2. Outliers

Graphic inspection for outliers will be performed. No data will be excluded from the primary and secondary analyses, including any outliers. Transformation on antibody titers during analysis can reduce the impact of the outliers. For continuous immunogenicity measures, non-parametric comparisons may be used as a sensitivity analysis if necessary.

3.4. Data Handling Conventions and Transformations

For the secondary analyses on booster response, baseline is defined as Year 4 post primary vaccination.

The neutralizing antibody titers will be transformed using \log_{10} transformation. Data will be back-transformed to the original scale for presentation.

3.5. Multicenter Studies

The primary and secondary analyses will not be adjusted by site.

3.6. Multiple Comparisons/Multiplicity

No multiplicity adjustments will be performed as most of the analyses will be descriptive in nature.

3.7. Interim Analysis

An interim analysis on immunogenicity assessment (anti-JE neutralizing antibody titer) collected at Visit 01 (Year 3 post primary immunization) will be conducted to gain knowledge on whether or not a booster JE vaccine needs to be given sooner. JE seroprotection rate, defined as the proportion of study participants with an anti-JE neutralizing antibody titer $\geq 1:10$ as measured by 50% plaque reduction neutralization test (PRNT-50), and geometric mean titer (GMT) of anti-JE neutralizing antibody at Visit 01 will be summarized by study group along with 95% CI. The group comparisons in terms of seroprotection rate and GMT will be provided. The analysis will be further stratified by the seroprotection status of participants on Day 28 post primary immunization in previous JEV05 study.

4. Subject Disposition

4.1. Subject Enrollment

Expected and actual subject enrollment will be tabulated by study group. The number and proportion of invited subjects meeting and not meeting entry criteria will also be tabulated.

4.2. Disposition of Subjects

Subject disposition will be summarized by study group. The following information will be tabulated.

- The number and proportion of subjects in ITT, PP, and safety analysis sets.
- The number and proportion of subjects who received a booster dose of CD-JEV.
- The number and proportion of subjects who are excluded from the ITT analysis and reasons for exclusion.
- The number and proportion of subjects who are excluded from the PP analysis and reasons for exclusion.
- The number and proportion of subjects who are excluded from the safety analysis and reasons for exclusion.
- The number and proportion of subjects who completed the study visit, as well as subjects who discontinued the study early and reasons for discontinuation.
- The number and proportion of subjects who have blood collection done at each applicable visit.
- The number and proportion of subjects who have valid serology results at each applicable visit.

Listings of subject disposition and status, exclusions from the ITT analysis, exclusions from the PP analysis, and exclusions from the safety analysis will be provided.

5. Subject Characteristics

5.1. Baseline Characteristics

Demographic and baseline characteristics collected at Visit 01, including age, gender at birth, weight, height, body temperature, blood pressure, pulse rate, and respiratory rate will be summarized by study group for the ITT and PP populations. Age, weight, length, body temperature, blood pressure, pulse rate, and respiratory rate will be described by number of subjects with data, mean, standard deviation (SD), median, minimum, and maximum. Gender at birth will be described by number and proportion of subjects in each study group. Denominators for proportions will be the number of subjects with non-missing values. T-test and Fisher's Exact Test will be used to confirm whether study groups of our interest are similar in terms of demographic and baseline characteristics.

In addition, immunization history, medical history, pre-existing conditions, and physical exam collected at Visit 01 will be summarized.

5.2. Subject Characteristics at Each Visit

Demographic characteristics, immunization history, medical history, pre-existing conditions, and physical exam collected at other visits will be summarized for ITT population by study group.

Listings of baseline demographics, immunization history, medical history, pre-existing condition, and physical exam at each applicable time points will be provided at participant-level.

6. Immunogenicity Analyses

The primary analysis will be conducted on the available immunogenicity data.

6.1. Immunogenicity Endpoints

The immunologic endpoints to assess the long-term antibody response of primary CD-JEV vaccination are as follows:

- Seroprotection rate at Year 3 (Visit 01) and Year 4 (Visit 02) post primary immunization, defined as the proportion of study participants with an anti-JE neutralizing antibody titer $\geq 1:10$ as measured by 50% plaque reduction neutralization test (PRNT-50).
- Geometric mean titer (GMT) of anti-JE neutralizing antibody at Year 3 and Year 4 post primary immunization as measured by PRNT-50.

The immunologic endpoints to evaluate the antibody response following a booster dose of CD-JEV are as follows:

- Seroprotection rate at 7 days after the booster dose (Visit 09) and 28 days after the booster dose (Visit 10), defined as the proportion of study participants with an anti-JE neutralizing antibody titer $\geq 1:10$ as measured by 50% plaque reduction neutralization test (PRNT-50).
- GMT of anti-JE neutralizing antibody at 7 days and 28 days after the booster dose as measured by PRNT-50.
- Seroconversion rate at 7 days and 28 days after the booster dose. For participants seronegative (participant with an anti-JE neutralizing antibody titer $< 1:10$ as measured by PRNT-50) at baseline (Year 4 post primary vaccination), seroconversion is defined as a change in serostatus from negative (anti-JE neutralizing antibody titer $< 1:10$) to positive (anti-JE neutralizing antibody titer $\geq 1:10$). For participants seropositive at baseline, seroconversion is defined as a 4-fold or higher response in anti-JE neutralizing antibody titer post booster dose in relation to pre-booster anti-JE neutralizing antibody titer.
- GMT ratio between 7 days after the booster dose and Year 4 (Visit 02) prior to booster dose and between 28 days after the booster dose and Year 4 (Visit 02) prior to booster dose.

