### **4.4. Study procedures**

#### **4.4.1. Recruitment and screening information**

Participants of JEV05 will be identified from the computerized HDSS database and dataset from the previous study maintained at the field site in Matlab and Mirpur. Field workers will visit their homes and explain to the parent or legal guardian the study purpose and procedures. If the parent or legal guardian is interested in having

their child participate in the study, field staff will invite them to come to their nearby FSC on a scheduled enrollment day.

All participants from JEV05 that continue to live in the study area are eligible to participate in this study. We propose to include children that were seronegative at 28 days because there is an indication from other studies that participants seronegative at D28 may generate a detectable antibody response at a later timepoint. Furthermore, we expect that some “seronegative” participants, can generate an anamnestic response. The serum collected at Day 7 following the booster dose will be used to determine whether previously vaccinated children who did not have any antibody at 3 and 4 years post CD-JEV vaccination can generate an anamnestic response (i.e., the children were immune to JE disease). Although serum neutralizing antibody is generally considered our best correlate of protection, there are instances where vaccinated persons without antibody level are nevertheless truly immune and they are able to mount a complete and normal immune response should they become infected. The way to determine this is to look at the anamnestic immune response, i.e., short-term antibody response. This is an antibody response that is not due to a new primary response; it depends on having primed B and T lymphocytes ready to respond quickly. The magnitude of the response measured between Day 7 and Day 28 will indicate whether the participant is mounting an anamnestic response to the booster or a primary response.

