- The difference in seroconversion rates between Groups A and B will be calculated along with the 95% CI of the difference using the Newcombe-Wilson method without continuity correction.
- The GMTs at 7 days and 28 days post the booster dose will be further compared to the GMTs at Year 4 prior to the booster dose using a paired t-test to evaluate the magnitude of increase in GMTs by study group. The GMT ratio between 7 days post the booster dose and Year 4 and between 28 days post the booster dose and Year 4 will be provided along with its 95% CI.
- Reverse cumulative distribution curves will be plotted for participants as anti-JE neutralizing antibody titer (x-axis) versus the proportion of participants with a titer of at least certain level (y-axis) at 7 and 28 days post the booster dose.

In addition, the booster response analyses on selected immunogenicity endpoints will be repeated on subgroups defined by seroprotection status of participants at Year 4 post primary CD-JEV vaccination.

Listing of serology results corresponding to each blood collection at participant-level will be provided.

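### In children negative at Year 4, one Year 4 reading is both selector and booster baseline and any later reading of 1:10 or more counts as seroconversion, so assay noise alone inflates the Day 7 rate

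*SAP*

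**What the plan says.** - **Baseline.** SAP 3.4: "For the secondary analyses on booster response, baseline is defined as Year 4 post primary vaccination". This is one blood draw, at Visit 02.
- **Seroconversion, negatives.** SAP 6.1: for a child below 1:10 at that draw, "seroconversion is defined as a change in serostatus from negative" to positive, that is, any later reading of 1:10 or more.
- **Seroconversion, positives.** SAP 6.1: "For participants seropositive at baseline, seroconversion is defined as a 4-fold or higher response in anti-JE neutralizing antibody titer".
- **Subgroups.** SAP 6.2: selected booster analyses "will be repeated on subgroups defined by seroprotection status of participants at Year 4 post primary CD-JEV vaccination". The same reading does the selecting.
- **Year 3 titre.** It enters the persistence endpoints ("Seroprotection rate at Year 3 (Visit 01) and Year 4 (Visit 02) post primary immunization") and the interim analysis in SAP 3.7. It enters no booster-response definition.
- **The question asked of Day 7.** Protocol 4.4.1 says the Day 7 serum will show whether "previously vaccinated children who did not have any antibody at 3 and 4 years post CD-JEV vaccination can generate an anamnestic response".
- **Control.** Under Protocol section 4 both groups get the booster and there is no placebo arm.
- **Exploratory analysis.** SAP 6.3.2 defines a primed group that must be IgM-negative before the booster and at Day 7 and must show a 4-fold neutralizing rise at Day 7. Only GMTs and GMT ratios are planned for it. The SAP assigns no value to a titre below 1:10.

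**The concern.** A child whose true titre lies near 1:10 may read just below it at Year 4 by chance. That child is then classed as negative and needs only to read 1:10 or above a week later to be counted as a converter. Children whose error went the other way are placed in the positive subgroup, where a 4-fold rise is required. The errors therefore do not cancel within the negatives: the bias runs upward.

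Among Year 4 negatives, Day 7 seroprotection and Day 7 seroconversion are the same quantity, so the subgroup proportion is exposed whichever of the two is tabulated. With no unboosted children, the noise component can be neither seen nor subtracted. The bias leans towards concluding that children without detectable antibody are still primed, in a study meant to inform policy on whether and when to boost.

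**Working it through.** **The plan's own figures.** The documents give no figure for seroconversion or assay repeatability. The one related calculation is SAP Table 2, the 95% CI width of pre-booster seroprotection. It reproduces in all 40 cells with the Wilson width 2z√(p(1−p)/n + z²/(4n²))/(1 + z²/n), n rounded down. For Group A, 60% and 20% attrition, n = 524 and the width is 0.084, as printed. Table 2 is sound, and its 40-80% range is used below.

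**Inputs**
- Seroprotected at Year 4: p = 40, 60 or 80% (SAP Table 2).
- Total SD of log10 titre, T: from the JEV05 Day 28 new-facility GMT interval 49.5-63.8, n = 581 (Protocol 3.4, Table 2). (1.8048 − 1.6946)/(2 × 1.96) × √581 ≈ 0.68. Using it at Year 4 is an assumption.
- Repeat-test SD, e: 0.1, 0.2 or 0.3 log10. Assumption.
- Fall from Year 3 to Year 4: 0.1 log10. Assumption.
- Booster effect: none. Errors normal and independent between draws.

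**Formula.** Mean log10 titre μ = 1 + T·Φ⁻¹(p). Correlation of two readings ρ = 1 − e²/T². With a = (1 − μ)/T and b = (log10 of the Day 7 threshold − μ)/T, the false conversion rate is 1 − Φ₂(a, b; ρ)/Φ(a). For children negative at both years, use the three-reading version with Year 3 limit a − 0.1/T.

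**Worked case**, p = 60%, e = 0.2: μ = 1 + 0.68 × 0.253 = 1.172; ρ = 1 − 0.04/0.4624 = 0.9135; Φ₂ = 0.3354; Φ(a) = 0.40; rate = 1 − 0.3354/0.40 = 16.1%.

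**Noise-only Day 7 conversion, % (p = 40/60/80%)**

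| Rule | e = 0.1 | e = 0.2 | e = 0.3 |
|---|---|---|---|
| Year 4 negative, Day 7 ≥1:10 (SAP) | 5.4/8.0/11.6 | 10.8/16.1/23.3 | 16.3/24.4/35.0 |
| Year 4 negative, Day 7 ≥1:20 | 0.1/0.1/0.2 | 1.8/3.1/5.1 | 5.3/9.0/14.7 |
| Negative both years, Day 7 ≥1:10 | 1.4/2.1/3.1 | 4.8/7.1/10.3 | 8.9/13.2/19.0 |
| Negative both years, Day 7 ≥1:20 | 0.0/0.0/0.0 | 0.4/0.7/1.1 | 2.0/3.3/5.3 |

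The 1:20 threshold is a 4-fold rise if 5 is the value assigned to readings below 1:10.

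At e = 0.2 the 4-fold rule in Year 4 positives yields only 0.9-1.3% by noise. The both-years subgroup keeps 84/76/67% of Year 4 negatives.

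**In children.** Group A, n = 524, p = 60%, e = 0.2: 0.40 × 524 ≈ 210 Year 4 negatives, of whom 0.161 × 210 ≈ 34 convert on noise alone. With the 1:20 threshold it is 0.031 × 210 ≈ 7.

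**Sensitivity.** With T = 0.6 or 0.8 and no fall between years, the SAP rule gives 4.6-39.7% and the both-years rule 2.4-25.6%, a relative cut of about 35-48%.

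**The case against.** - **The plan already has a 4-fold rule.** The primary-versus-secondary question is handled in SAP 6.3.2, and Protocol 4.4.1 says the magnitude of the response is what distinguishes the two. This stands in part. A reader might infer that Day 7 seroconversion is the plan's only evidence of memory; it is not. But SAP 6.3.2 plans no proportion of negatives who are primed, and a fold rise from below 1:10 is undefined until a value is assigned.
- **The size rests on an unseen input.** This stands. If half the negatives have no antibody at all, the rates roughly halve. Protocol 4.5.3.3 ships sera after each study year, so Year 4 and Day 7 samples could be tested together, although that is not stated. If they shared half the error variance, 16% would fall to about 11%. The direction does not change.
- **The protocol mismatch is thin.** The phrase "children who did not have any antibody at 3 and 4 years post CD-JEV vaccination" comes from the recruitment rationale. Protocol 6.1 compares Day 7 and Day 28 with Year 4 only, and the SAP follows it. This stands: the SAP does not contradict the protocol's analysis section, but the stated Day 7 population goes unreported.
- **Selecting on both years changes the question.** It removes children who truly waned between Year 3 and Year 4 and are negative when boosted. This stands and argues against making it the main subgroup.
- **The study is descriptive.** No decision rule uses this rate, and paired GMT ratios, reverse cumulative curves and listings are planned. This lowers the stakes but does not remove the bias from a headline proportion.

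**Conclusion.** The point holds. Using one reading as selector and baseline, with no minimum rise for negatives and no unboosted arm, biases Day 7 seroconversion in Year 4 negatives upward. On the assumptions listed, noise alone gives about 5-35%, and 11/16/23% at repeat-test SD 0.2. The direction is secure; the size depends mainly on an assay error that the documents do not report.

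A reader might go further and infer that the Year 3 titre lies unused and would prevent the problem. The documents and figures do not support that. Year 3 is analysed for persistence and at the interim; it is absent only from the booster definitions. Requiring both years negative leaves 5/7/10% at SD 0.2, so it only about halves the artefact, whereas a 1:20 threshold in the planned subgroup leaves 2/3/5%. Nor is the subgroup confined to readings just under 1:10: it takes every reading below the cutoff, and the artefact comes from the children near it.

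This is a cheap improvement to the interpretation of a secondary result, not a flaw in the persistence analysis.

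**What to change.** 1. Keep the Year-4-negative subgroup and the existing seroconversion table.
2. In SAP 3.4, state the value assigned to titres below 1:10. This also makes the fold rise in SAP 6.1 and 6.3.2 defined for negatives.
3. In SAP 6.2, add for Day 7 the share of Year 4 negatives, with 95% CI, whose titre is at least 4 times that value (1:20 if 5 is used).
4. Add a sensitivity table for children below 1:10 at both Year 3 and Year 4, the population named in Protocol 4.4.1, under both the 1:10 and the 4-fold criterion. With 1:20, noise is about 1% or less at SD 0.2.

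**Cost.** SAP wording and two short tables; the samples are already scheduled. The 4-fold criterion misses small true responses. The both-years subgroup keeps about 67-84% of Year 4 negatives at SD 0.2 and leaves out children who truly waned in the last year, so it should stay a sensitivity analysis.

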6.2. Analysis of Immunogenicity Endpoints

To assess the long-term antibody response three and four years after primary CD-JEV vaccination, the following analyses will be conducted,

- The number and proportion of participants with an anti-JE neutralizing antibody titer $\geq 1:10$ will be tabulated by study group at Year 3 and Year 4 post primary immunization. The 95% CI of the proportion will be provided using Wilson score method without continuity correction [1, 2].
- The difference in JE seroprotection rates between Groups A and B will be calculated along with the 95% CI of the difference using the Newcombe-Wilson method without continuity correction [3].
- GMTs of the anti-JE neutralizing antibody response and their associated 95% CI will be calculated at Year 3 and Year 4 post immunization.
- The GMTs will be compared between Groups A and B using t-test at each applicable time point. The ratio of the GMTs along with its 95% CI will be provided.
- Reverse cumulative distribution curves will be plotted for participants as anti-JE neutralizing antibody titer (x-axis) versus the proportion of participants with a titer of at least certain level (y-axis) at Year 3 and Year 4.

To evaluate the antibody response following a booster dose of CD-JEV given at five years of age, the following analyses will be performed,

- The number and proportion of participants with an anti-JE neutralizing antibody titer $\geq 1:10$ will be tabulated by study group at 7 days after the booster dose and 28 days after the booster dose. The 95% CI of the proportion will be provided using Wilson score method without continuity correction.

- The difference in JE seroprotection rates between Groups A and B will be calculated along with the 95% CI of the difference using the Newcombe-Wilson method without continuity correction.
- GMTs of the anti-JE neutralizing antibody response and their associated 95% CI will be calculated at 7 days and 28 days post the booster dose.
- The GMTs will be compared between Groups A and B using t-test at each applicable time point. The ratio of the GMTs along with its 95% CI will be provided.
- The number and proportion of participants with seroconversion will be tabulated by study group at 7 days and 28 days after the booster dose. The 95% CI of the proportion will be provided using Wilson score method without continuity correction.
- The difference in seroconversion rates between Groups A and B will be calculated along with the 95% CI of the difference using the Newcombe-Wilson method without continuity correction.
- The GMTs at 7 days and 28 days post the booster dose will be further compared to the GMTs at Year 4 prior to the booster dose using a paired t-test to evaluate the magnitude of increase in GMTs by study group. The GMT ratio between 7 days post the booster dose and Year 4 and between 28 days post the booster dose and Year 4 will be provided along with its 95% CI.
- Reverse cumulative distribution curves will be plotted for participants as anti-JE neutralizing antibody titer (x-axis) versus the proportion of participants with a titer of at least certain level (y-axis) at 7 and 28 days post the booster dose.

In addition, the booster response analyses on selected immunogenicity endpoints will be repeated on subgroups defined by seroprotection status of participants at Year 4 post primary CD-JEV vaccination.

Listing of serology results corresponding to each blood collection at participant-level will be provided.

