### 3.4. Study rationale

In 2012 PATH sponsored a double-blind, randomized controlled trial among 818 Bangladeshi infants aged 10 to 12 months to compare the immunogenicity of three lots of live attenuated CD-JEV manufactured in the Chengdu Institute of Biological Products' (CDIBP) newly constructed GMP facility and one control lot of CD-JEV manufactured in the pre-existing facility. The study was conducted in rural Matlab and in Mirpur, in urban Dhaka. All four lots of JE vaccine were well-tolerated by the Bangladeshi infants ("A clinical trial in healthy infants to assess lot-to-lot consistency of Japanese encephalitis live attenuated SA 14-14-2 vaccine manufactured in a new good manufacturing practice facility and non-inferiority with respect to an earlier product", icddr,b Protocol # 11050). Seroprotection rates (anti-JE neutralizing antibody titer  $\geq 1:10$ ) ranged from 80% to 86% for all four lots of vaccine, with an average GMT of 56 (Table 2).

**Table 2. Seroprotection rates and geometric mean antibody titers measured at 28 days post vaccination by treatment group (per protocol population).**

Study group (N)	Group 1 (146)	Group 2 (195)	Group 3 (192)	Group 4 (194)	New Facility Group 2-4 (581)
Number of seroprotected children (%)	126 (86.3)	160 (82.1)	154 (80.2)	164 (84.5)	478 (82.3)
95% Confidence intervals	79.8–91.0	76.1–86.8	74.0–85.2	78.8–89.0	79.0–85.2
Geometric mean antibody titer	77.3	52.8	53.4	62.8	56.2
95% Confidence intervals	59.6–100.4	42.9–65.1	42.4–67.2	50.3–78.4	49.5–63.8

Group 1 represents the existing facility lot; Groups 2, 3 and 4 the new facility lots.  
Seroprotection defined as JE neutralizing antibody titer  $\geq 1:10$

This study was a requirement for WHO-prequalification; based on these data the vaccine was prequalified in October 2013. However, these GMT and seroprotection rates were lower than those seen in other study populations, including the study referenced above that was conducted in Philippines, which used the same reference laboratory to test the samples. While other study factors, such as the vaccine stability or lots used, may account for the results, different populations may respond differently to vaccines. For example, Bangladeshi children have been shown to have lower immune responses to other vaccines, including oral rotavirus vaccines, as compared to children in higher-resource settings.

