2.3. Sample Size and Power

Since the study aims at following up with the participants of the JEV05 study who received a single dose of CD-JEV between 10 and 12 months of age, a maximum of 818 former JEV05 participants (up to 655 in Group A and up to 163 in Group B) is expected to be enrolled in this study. We anticipate an attrition rate from 10% to 40% in both groups, i.e. 10% to 40% of the subjects in Group A and Group B may not be enrolled into this study.

The precision (width) of the 95% confidence interval (CI) of the seroprotection rate before a booster vaccination is calculated based upon different assumptions on attrition rate and expected seroprotection rates and provided in Table 2.

Table 2. Precision of the 95% CI of the seroprotection rate according to attrition rate and seroprotection rate in each study group

Study Group	Expected seroprotection rate	Attrition rate			
		10%	20%	30%	40%
Group A	40%	0.079	0.084	0.089	0.096
	50%	0.080	0.085	0.091	0.098
	60%	0.079	0.084	0.089	0.096
	70%	0.074	0.078	0.084	0.090
	80%	0.065	0.068	0.073	0.079
Group B	40%	0.157	0.166	0.177	0.191
	50%	0.160	0.169	0.181	0.195
	60%	0.157	0.166	0.177	0.191
	70%	0.147	0.156	0.166	0.180
	80%	0.129	0.137	0.146	0.158

3. General Considerations for Data Analyses

All statistical tests will be two-sided with a significance level of 0.05. P-values will be recorded to 4 decimal places. All analyses will be conducted using SAS.

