3.2. Adjustment for Covariates

No adjustment for covariates is planned. However, longitudinal analysis may be performed for the long-term assessment of the anti-JE antibody response to CD-JEV as an ad-hoc analysis if necessary. If the longitudinal analysis is conducted, duration of follow-up since the initial vaccination will be included in the analysis as covariates. Other variables (e.g., gender, study site, nutrition status) as appropriate will be evaluated for inclusion as covariates as well. The longitudinal analyses will be considered exploratory and will not replace the primary planned analysis.

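### The post-booster GMT comparison of Groups A and B takes no account of the Year 4 titre, so it measures total titre difference and should not be read as a difference in booster response

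*SAP*

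**What the plan says.** SAP 6.2 introduces its booster analyses with "To evaluate the antibody response following a booster dose of CD-JEV given at five years of age, the following analyses will be performed". The list that follows includes "The GMTs will be compared between Groups A and B using t-test at each applicable time point", with the GMT ratio and its 95% CI. The same sentence appears earlier in 6.2 for Year 3 and Year 4, where no pre-booster baseline applies; this point concerns only Day 7 and Day 28. Protocol 6.1 plans the same t-test.

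Three other statements bear on it:

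- SAP 3.4: "For the secondary analyses on booster response, baseline is defined as Year 4 post primary vaccination".
- SAP 3.2: "No adjustment for covariates is planned". The one model it allows is optional and concerns persistence: "longitudinal analysis may be performed for the long-term assessment of the anti-JE antibody response to CD-JEV as an ad-hoc analysis if necessary".
- SAP section 3: "All statistical tests will be two-sided with a significance level of 0.05".

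The Year 4 titre is used elsewhere in the booster analyses:

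- Fold rise from Year 4 is estimated and tested by paired t-test, within each group only.
- Seroconversion is defined against the Year 4 titre (SAP 6.1) and compared between groups with a Newcombe-Wilson interval (SAP 6.2).
- Some booster endpoints, not named, are repeated by Year 4 seroprotection status.

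**The concern.** Children who start higher at Year 4 may also end higher at Day 7 and Day 28, even if both groups respond to the booster in the same way. An unadjusted post-booster ratio then combines what was left from the primary dose with what the booster added. Because the ratio is listed under booster response, a reader may take it as evidence that one group boosts better.

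There is a documented reason to expect unequal starting levels. In Protocol 3.4, Table 2, the row "Geometric mean antibody titer" gives 77.3 for JEV05 Group 1 (now Group B) and 56.2 for the pooled new-facility groups (now Group A).

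The other planned analyses do not settle the matter. Seroconversion is a yes/no measure whose threshold changes with baseline: a seronegative child need only reach 1:10, while a seropositive child needs a fourfold rise. Fold rise is not compared between groups. Serostatus strata leave the variation in titre above 1:10 untouched.

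**Working it through.** **Figures in the plan.** The documents give no power or precision for the A versus B GMT contrast, and Protocol section 5 states that no sample size was calculated. The nearest figure is SAP Table 2, on seroprotection. All 40 cells reproduce as full Wilson widths with the group size rounded down. For example, at a 50% rate and 20% attrition the width is 1.96/√(n + 1.96²): 0.085 for n = 524 and 0.169 for n = 130, as printed. Those group sizes are used below.

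**Step 1. JEV05 Day 28 gap (Protocol Table 2).** SD of log10 titre = CI half-width × √n / t.

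- Group 1: n = 146, CI 59.6 to 100.4, SD 0.692.
- New facility: n = 581, CI 49.5 to 63.8, SD 0.676.
- Pooled SD 0.68. The n-weighted log mean of 52.8, 53.4 and 62.8 gives 56.2, as printed.
- B/A = 77.3/56.2 = 1.38, log10 = 0.138. SE = 0.68 × √(1/146 + 1/581) = 0.063. The 95% CI is 1.03 to 1.83, p = 0.028.

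**Step 2. Does such a gap last?** The documents give no Year 4 titres by group. The only longitudinal group titres are in Protocol Table 1 (Philippines):

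| Ratio | Day 28 | Year 2 | Year 3 |
|---|---|---|---|
| Group 1 / Group 2 | 202.8/155.0 = 1.31 | 68.8/61.6 = 1.12 | 49.9/45.7 = 1.09 |
| Group 1 / Group 3 | 202.8/139.4 = 1.45 | 68.8/70.1 = 0.98 | 49.9/59.3 = 0.84 |

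The first gap fell to about a third of its log size (ln 1.09 / ln 1.31 ≈ 0.33). The second reversed. These are different groups with wide intervals, so they show only that persistence cannot be taken for granted.

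**Step 3. Carry-over with identical boosting.** Unadjusted post-booster ratio = (Year 4 ratio)^slope. SE = 0.68 × √(1/524 + 1/130) = 0.0666 on the log10 scale. The chance of p < 0.05 is by normal approximation. The slope (taken equal to the correlation r), the persistence and the post-booster SD of 0.68 are assumptions.

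| Share of log gap left at Year 4 | Slope 0.3 | Slope 0.5 | Slope 0.7 |
|---|---|---|---|
| All (ratio 1.38) | 1.10, 10% | 1.17, 18% | 1.25, 31% |
| Half (1.17) | 1.05, 6% | 1.08, 8% | 1.12, 11% |
| A third (1.11) | 1.03, 5.5% | 1.05, 6% | 1.08, 8% |

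A simulation of the top row (3,000 runs per cell, titres below 1:10 set to 5 as an assumption) gave p < 0.05 in 10%, 18% and 30% of trials for the t-test. For a model adjusting for log10 Year 4 titre it gave about 5% throughout, with A/B ratios of 0.985 to 0.993.

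**Step 4. Precision.** 95% CI factor = 10^(1.963 × 0.0666 × √(1 − r²)).

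| r | 0 | 0.3 | 0.5 | 0.7 |
|---|---|---|---|---|
| Factor | 1.35 | 1.33 | 1.30 | 1.24 |

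On the log scale the interval narrows by 0%, 5%, 13% and 29%. Comparing fold rise between groups would instead multiply the SE by √(2(1 − r)). At r = 0.3 that gives a factor of 1.43, wider than the t-test's; the two are equal at r = 0.5.

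**The case against.** The groups come from the JEV05 randomisation, and the Year 4 titre is a later result of the primary lot. The unadjusted ratio is therefore a legitimate total difference in post-booster level. Protocol section 1 defines no hypotheses and calls the study descriptive, and the secondary objective concerns boosted children generally rather than A against B. The Year 4 A/B ratio will be reported, so a carried-over gap will be visible beside the later ratios. All of this stands. It supports keeping the t-test, but it does not supply an estimate of booster response given the starting level.

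Four stronger readings are tempting, and the documents do not support them:

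- *The plan never compares booster response between groups.* It does, through seroconversion relative to Year 4. What is missing is a comparison of magnitude.
- *The 10 to 31% is inflated type I error.* The t-test's null is equal post-booster GMTs. If a gap carries over, that null is false and a rejection detects a real difference in titre. The mistake would be to attribute it to boosting.
- *The groups are known to differ at Year 4.* The known gap is at Day 28 after the primary dose, four years earlier, and Protocol Table 1 shows comparable gaps shrinking or reversing.
- *The interval is materially too wide.* The documents give no correlation. Protocol 4.4.1 expects some seronegative children to mount an anamnestic response, which would weaken dependence on the Year 4 titre. At r = 0 nothing is gained.

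**Conclusion.** The point holds as one of interpretation. The post-booster A versus B t-test is a valid comparison of titre level, but it is listed as an evaluation of booster response and ignores the baseline that the SAP itself defines. No other planned analysis gives the between-group difference in magnitude conditional on that baseline.

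The size is uncertain. With identical boosting the unadjusted ratio could be anywhere from 1.03 (a third of the JEV05 gap left, slope 0.3) to 1.25 (all of it left, slope 0.7). It would be 1.00 if no gap remains or the slope is zero. The precision argument is secondary: negligible to modest for r up to 0.5, and substantial only for higher values. The results rest on assumed persistence, slope and correlation, on a post-booster SD borrowed from JEV05 Day 28, and on 20% attrition. A supplementary model is worth adding because it is cheap and gives each ratio a clear meaning. The primary objective is unaffected.

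**What to change.** In SAP 6.2:

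- Keep the Day 7 and Day 28 t-tests and label their ratio *total difference in post-booster titre*.
- Add, at each time point, a linear model of log10 titre on group, log10 Year 4 titre and an indicator for a Year 4 titre below 1:10.
- Report the adjusted GMT ratio with its 95% CI beside the unadjusted one, labelled *booster response given pre-booster level*.
- Use this model in preference to a between-group comparison of fold rise, which loses precision when r is below 0.5.

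Amend SAP 3.2 to allow this one adjustment. No site term is needed for this purpose, so SAP 3.5 can stand. State in SAP 3.4 the value assigned to titres below 1:10, which it does not give, and name the endpoints to be repeated by Year 4 serostatus.

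The cost is a few lines of SAP text and one model per time point; the Year 4 titre is already collected. The drawback is that the Year 4 titre may itself be affected by the JEV05 lot. The adjusted ratio is therefore conditional and should be presented as supplementary, never alone.
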